15.6.3. Efficacy

Laboratory Parameters
Serum M-protein, Urine M-protein, Serum FLC

 • If a laboratory value which is expected to have a numeric value for summary purposes, has a non-detectable level reported in the database, where the numeric value is missing, but typically a character value starting with '<x' or '>x' (or indicated as less than x or greater than x in the comment field) is present, the number of significant digits in the observed values will be used to determine how much to add or subtract in order to impute the corresponding numeric value. 
 ○ Example 1: 2 Significant Digits = '< x' becomes x – 0.01 ○ Example 2: 1 Significant Digit = '> x' becomes x + 0.1 • Example 3: 0 Significant Digits = '< x' becomes x – 1

15.6.4. Safety

Adverse Events
AE'S of Special Interest

• Eye disorder (CTCAE)• Thrombocytopenia• Infusion-Related Reactions• Neutropenia• Corneal events (GSK scale): collected in Ocular form

15.7. Appendix 7: Reporting Standards for Missing Data

15.7.1. Premature Withdrawals

Element	Reporting Detail
General	
 • Subject study completion (i.e. as specified in the protocol) was defined as "A participant will be considered to have completed the study if he or she has received at least one dose of the study treatment and, has died or is still in follow-up when the study is closed, and has not withdrawn consent from study participation." • Withdrawn subjects will not be replaced in the study. • All available data from participants who were withdrawn from the study will be listed and all available planned data will be included in summary tables and figures, unless otherwise specified. • Withdrawal visits will be slotted as per Appendix 3: Assessment Windows or will be summarised as withdrawal visits.

15.7.2. Handling of Missing Data

Element	Reporting Detail
General	
 • Missing data occurs when any requested data is not provided, leading to blank fields on the collection instrument: 
 ○ These data will be indicated by the use of a "blank" in subject listing displays. Unless all data for a specific visit are missing in which case the data is excluded from the table. ○ Answers such as "Not applicable" and "Not evaluable" are not considered to be missing data and should be displayed as such.
Outliers	
 • Any participants excluded from the summaries and/or statistical analyses will be documented along with the reason for exclusion in the clinical study report.
Responder Analysis	
 • For endpoints which determine the percentage of responders, subjects with unknown/not evaluable or missing best overall response will be assumed to be non-responders and will be included in the denominator when calculating the percentages.
Time to Event	
 • Because study treatment is dependent on the study endpoints (e.g., progression, i.e. not a fixed treatment duration), the length of treatment for each subject will depend on the efficacy and toxicity of the treatment, so the duration of treatment will vary across subjects. Similarly, the duration of follow up will also vary. All available time-to-event data will be analysed using suitable statistical methods; subjects with shorter treatment and follow-up due to the natural history of their disease or medical necessities of the treatment of their disease will not be considered to have missing time-to-event data.

15.7.2.1. Handling of Missing and Partial Dates

Element	Reporting Detail
General	
 • Partial dates will be displayed as captured in subject listing displays. • Imputed partial dates will not be used to derive study day, duration (e.g. duration of adverse events), or elapsed time variables. In addition, imputed dates are not used for deriving the last contact date in the overall survival analysis dataset. • Imputed dates will not be displayed in listings. However, where necessary, display macros may impute dates as temporary variables for the purpose of sorting data in listings only. In addition, partial dates may be imputed for 'slotting' data to study time periods or for specific analysis purposes as outlined below.

Element	Reporting Detail
Adverse Events	
 • The eCRF allows for the possibility of partial dates (i.e., only month and year) to be recorded for AE start and end dates; that is, the day of the month may be missing. 
 ○ Missing Start Day: First of the month will be used unless this is before the start date of study treatment; in this case the study treatment start date will be used and hence the event is considered On-treatment as per Appendix 4: Study Phases and Treatment Emergent Adverse Events. ○ Missing Stop Day: Last day of the month will be used. • Completely missing start dates will remain missing, with no imputation applied. Consequently, time to onset and duration of such events will be missing. • Completely or partially missing end dates will remain missing, with no imputation applied. Consequently, duration of such events will be missing.
Concomitant Medications/ Medical History	
 • Partial dates for any concomitant medications recorded in the CRF will be imputed using the following convention: 
 ○ If the partial date is a start date, a '01' will be used for the day and 'Jan' will be used for the month ○ If the partial date is a stop date, a '28/29/30/31' will be used for the day (dependent on the month and year) and 'Dec' will be used for the month. • The recorded partial date will be displayed in listings.
New Anti-Cancer Therapy/ Radiotherapy/ Surgical Procedures for Efficacy Evaluation (e.g., response rate, time to event)	
 • Start dates for follow-up anti-cancer therapy, radiotherapy (where applicable), and surgical procedures (where applicable) will be temporarily imputed in order to define event and censoring rules for progression-free survival, response rate, time to progression, duration of response or time to response (i.e. start date for new anti-cancer therapy). The imputed dates will not be stored on the anti-cancer therapy, radiotherapy, or surgical procedure datasets. • If missing start day, month, and year, then no imputation for completely missing dates • If missing start day and month, then no imputation should be done • If missing start day, then do the following: 
 • If partial date falls in the same month as the last dose of study treatment, then assign to earlier of (date of last dose of study treatment+1, last day of month). • If partial date falls in the same month as the subject's last assessment and the subject's last assessment is PD, then assign to earlier of (date of PD+1, last day of month). • If both rules above apply, then assign to latest of the 2 dates • Otherwise, impute missing day to the first of the month. • If missing end date, then no imputation should be done.
Covariates for efficacy analysis (Date of initial diagnosis/ Last recurrence/ Last progression)	
 • If both month and day are missing, first of January will be used • If only day is missing, first of the month will be used
Treatment end date	
 • If there is more than one study treatment, imputation of missing treatment end date will be applied to all applicable treatments following rules below and treatment end date is the latest treatment end date across all study treatments. In general, completely missing

Element	Reporting Detail
	
end dates are not imputed, with the following exceptions for imputation of missing treatment end date at interim analyses.
 
 • For imputation of missing exposure end date at an interim analysis when subjects are still on treatment, the following conventions will be applied: 
 ○ If the missing end date is in the last exposure record, the earliest of: the date of the data cut-off, the date of withdrawal from the study, or the death date will be used ○ If the missing end date is not in the last exposure record, treatment start date for the record will be used • The imputed treatment end date will be used to calculate cumulative dose and duration of treatment as specified in Section 15.6.2 
If treatment end date is missing for a cycle, treatment start date for the cycle will be used.

PACT	
 • For PACT subjects, subject's last Visit date will be used as subject's end of study date, wherever required.

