Outcome of first occurrence [1] (n=xx)			
Resolved	XX (XX.X%)	XX (XX.X%)	XX (XX.X%)
re-started with dose delay and reduction	XX (XX.X%)	XX (XX.X%)	XX (XX.X%)
re-started with dose delay but no reduction	XX (XX.X%)	XX (XX.X%)	XX (XX.X%)
re-started with dose reduction but no delay	XX (XX.X%)	XX (XX.X%)	XX (XX.X%)
re-started without dose delay or reduction	XX (XX.X%)	XX (XX.X%)	XX (XX.X%)
not re-started	XX (XX.X%)	XX (XX.X%)	XX (XX.X%)
Not resolved, re-started	XX (XX.X%)	XX (XX.X%)	XX (XX.X%)

CONFIDENTIAL

205678

with dose delay and reduction	XX (XX.X%)	XX (XX.X%)	XX (XX.X%)
with dose delay but no reduction	XX (XX.X%)	XX (XX.X%)	XX (XX.X%)
with dose reduction but no delay	XX (XX.X%)	XX (XX.X%)	XX (XX.X%)
without dose delay or reduction	XX (XX.X%)	XX (XX.X%)	XX (XX.X%)
Not resolved, not re-started	XX (XX.X%)	XX (XX.X%)	XX (XX.X%)
not discontinued	XX (XX.X%)	XX (XX.X%)	XX (XX.X%)
discontinued, follow up ongoing	XX (XX.X%)	XX (XX.X%)	XX (XX.X%)
discontinued, follow up ended	XX (XX.X%)	XX (XX.X%)	XX (XX.X%)
Duration of first occurrence [1] [2]			
n	XX	XX	XX
Mean	XX.X	XX.X	XX.X
SD	XX.XX	XX.XX	XX.XX
Median	XX.X	XX.X	XX.X
Min.	XX	XX	XX
Max.	XX	XX	XX
Number of occurrences (based on subjects with the event)			
One	XX (XX.X%)	XX (XX.X%)	XX (XX.X%)
Two	XX (XX.X%)	XX (XX.X%)	XX (XX.X%)
Three or more	XX (XX.X%)	XX (XX.X%)	XX (XX.X%)
Outcome post treatment exposure			
Number of of subjects with unresolved Event at the end of treatment exposure, or with event onset post treatment exposure.	xx	xx	xx
Resolved	XX (XX.X%)	XX (XX.X%)	XX (XX.X%)
Not resolved, follow up ongoing	XX (XX.X%)	XX (XX.X%)	XX (XX.X%)

Not resolved, follow up ended	XX (XX.X%)	XX (XX.X%)	XX (XX.X%)
Time to resolution post treatment exposure, days			
n	XX	XX	XX
Mean	XX.X	XX.X	XX.X
SD	XX.XX	XX.XX	XX.XX
Median	XX.X	XX.X	XX.X
Min.	XX	XX	XX
Max.	XX	XX	XX

[1] The duration is defined as time from onset of any **blurred vision** event to the first time the subject is free of any such event. It requires at least one day gap between the resolution of all events from first occurrence to the onset of second occurrence.

[2] Imputed AE stop date was used in the calculation of duration if the outcome of the event was resolved/resolved with sequelae and AE stop date was partial with day missing. Imputed AE start date was used in the calculation if the start date was partial with day missing.

[3] The end of treatment exposure is defined as last infusion date +20 days.

Programming note:

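### The AE partial-date rules conflict on whether a day-missing stop date is imputed and used for duration, and the start rule can turn events from months before first dose into on-treatment events

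*SAP*

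**What the plan says.** Four statements bear on an AE whose stop date has month and year but no day. Three are in SAP Section 15.7.2.1 and one is in Appendix 14 (Section 15.14).

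- **Adverse Events row, missing stop day:** "Last day of the month will be used".
- **Adverse Events row, last bullet:** "Completely or partially missing end dates will remain missing, with no imputation applied", followed by "Consequently, duration of such events will be missing".
- **General row:** "Imputed partial dates will not be used to derive study day, duration (e.g. duration of adverse events), or elapsed time variables". The same row adds that "partial dates may be imputed for 'slotting' data to study time periods or for specific analysis purposes as outlined below".
- **Shell SAFE_T21, footnote [2]:** "Imputed AE stop date was used in the calculation of duration if the outcome of the event was resolved/resolved with sequelae", provided only the day is missing. For starts it says "Imputed AE start date was used in the calculation if the start date was partial with day missing".

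For a missing start day, the Adverse Events row takes the first of the month. If that falls before study treatment began, "in this case the study treatment start date will be used", and the row states that the event then counts as on-treatment under Appendix 4.

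**The concern.** A programmer cannot follow all four statements. The Adverse Events row itself describes a partial date as one with only the day missing, so its two stop-date bullets govern the same record and give opposite instructions. On duration, the section and the shell disagree. SAFE_T21 is the shell for the CTCAE eye-event tables 3.0200-3.0204 (keratopathy, dry eye, blurred vision, photophobia and eye pain), and these are adverse events of special interest.

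The start rule is a separate fault. It compares the first of the month with the first-dose date and nothing else. It does not ask whether the event's month is the month of first dose, or whether a recorded stop date already precedes first dose. An event known to predate treatment can therefore be reported as on-treatment.

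**Working it through.** The SAP gives no figure to reproduce here, so the rules are set side by side and then applied literally to illustrative dates. The dates are assumptions and do not come from the SAP.

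**1. Stop day missing: what each statement yields**

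| Source | Stop date | Duration |
|---|---|---|
| 15.7.2.1, AE row, missing-stop-day bullet | month end | not stated |
| 15.7.2.1, AE row, last bullet | stays missing | missing |
| 15.7.2.1, General row | may be imputed for other purposes | imputed date not allowed |
| SAFE_T21 footnote [2], resolved events | imputed | calculated from the imputed date |

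Within Section 15.7.2.1 the contradiction is whether a date is imputed at all. On duration the section is consistent (missing), and the shell contradicts it.

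**2. Size for one event.** Duration = stop - start + 1. Take onset on 15 September and a stop recorded as October.

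- Stop imputed to 31 October: 47 days.
- Section 15.7.2.1: missing.
- True stop on 1 October: 17 days. True stop on 31 October: 47 days. The truth therefore lies between 17 and 47 days.

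Month-end imputation never understates the stop. In a month of n days the excess runs from 0 to n - 1. If the true day is uniform over the month (assumption), the mean excess is (n - 1)/2: 14.5 days for n = 30 and 15.0 days for n = 31.

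**3. Start day missing: the rule applied literally.** Assume first dose on 20 September 2018.

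| Recorded start | First of month | Date assigned | Class |
|---|---|---|---|
| June 2018 | 1 June | 20 September | on-treatment |
| August 2018 | 1 August | 20 September | on-treatment |
| September 2018 | 1 September | 20 September | on-treatment |
| October 2018 | 1 October | 1 October | on-treatment |

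The September row is truly ambiguous, and moving it to first dose is a usual conservative convention. The June and August rows are wrong: those months ended before treatment began. Section 15.4.2 flags an event as treatment-emergent when its start is on or after treatment start, so both would be flagged.

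**4. Start after stop.** With a start recorded as August 2018 and a complete stop of 5 September 2018, the assigned start is 20 September. If imputed starts enter duration, as footnote [2] allows, the result is 5 - 20 + 1 = -14 days.

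**5. The missing condition is used elsewhere.** The new anti-cancer therapy row of the same table tests whether a partial date falls in the same month as a reference date. The AE start rule has no such test.

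**The case against.** The best defence is the General row's allowance for assigning data to study periods or for listed purposes. On that reading the AE day is imputed only to place the event in a period, and durations stay missing, as the General row and the last AE bullet both say. The outlier would then be one footnote in an example shell. This explains why a stop day might be imputed at all. It does not square imputation with a bullet that says none is applied, and the AE row lists no duration purpose that would license the footnote.

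It is also fair to say that the start-rule error needs AEs with onset in a calendar month before first dose and no recorded day. Whether such events are collected is a protocol matter not shown here. The negative duration arises only if imputed starts are used in durations, which the General row forbids.

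Three stronger inferences are tempting, and the SAP does not support them:

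- **That onset-and-duration tables on shell ESI2b drop these events while SAFE_T21 counts them, so one report gives two durations for one event.** The notes to Tables 3.0290, 3.0330, 3.0890, 3.0360 and 3.0910 defer the duration algorithm to another study's table, which is not shown and may agree with SAFE_T21. The clear overlap between the two shells is GSK-scale corneal events (Tables 3.0910 and 3.0911). Those come from the Ocular form, so the AE date rules do not plainly apply to them.
- **That the SAFE_T21 rule moves subjects between the 1-21, 22-42 and >42 day duration bands.** Section 8.2.1 sets those bands for thrombocytopenia, infusion-related reactions and neutropenia. SAFE_T21 gives duration as n, mean, SD, median, minimum and maximum; its bands are for time to onset.
- **That some stated share of durations changes.** The SAP gives no count of partial dates, so any percentage would be an assumption repeated as a result.

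**Conclusion.** The point holds as two wording faults with real consequences for derivation. First, the stop-date statements cannot all be followed, and a CTCAE eye-event duration in Tables 3.0200-3.0204 is missing under Section 15.7.2.1 but counted under the shell. Second, the start rule, read literally, gives a wrong classification for any day-missing event whose month precedes the month of first dose or whose recorded stop precedes first dose.

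For a single event the stop-date choice can mean 47 days against no value, on the illustrative dates above. The total effect cannot be sized: it depends on how many AEs have partial dates and whether pre-treatment onsets are recorded, and the SAP gives neither. The outputs concerned are descriptive summaries of AE onset, duration and treatment emergence. The primary ORR analysis is unaffected. The text should be corrected, but nothing here bears on the efficacy conclusion.

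**What to change.** 1. **Start rule.** Limit the first-dose substitution to partial starts in the same month and year as first dose with no recorded stop before first dose. Otherwise use the first of the month. In the illustration, the June and August events then fall before treatment.
2. **Stop rule.** State one rule and carry it through the General row, the AE row and SAFE_T21 footnote [2]. Either option is valid:
   - *Period assignment only.* Imputed dates place events in study periods, and durations from partial dates stay missing. Correct footnote [2], and reword the last AE bullet so that it no longer denies the month-end imputation.
   - *Use for duration.* For resolved events with only the stop day missing, impute the earlier of month end, death and data cut-off, and use that date for duration in all AE tables. Delete 'or partially' from the last AE bullet and exempt AE duration from the General bar. Say also whether an imputed start may be used for time to onset.

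The first option is the smaller edit. The second keeps more events but overstates their duration on average. Either costs a few lines of SAP text and one shared date derivation, with no new data.

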1. Subsequent disease assessment is defined as the next adequate (not missing or NE) disease assessment following the first timepoint before (or on the same date of) start of new anti-cancer therapy except for confirmation of PD, for which PD or death due to PD after new anti-cancer therapy are considered for confirmation of PD. No minimal time interval is required for the subsequent disease assessment, but a different sample is required for confirmation.
2. SD does not need to be confirmed.
3. PD due to imaging (i.e., plasmacytoma or bone lesion) does not need to be confirmed.
4. Where criteria are not mutually exclusive, take the first that applies.

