7.2.1.5. Progression Free Survival (PFS)

PFS is defined as the time from randomization until the earliest date of confirmed PD per IMWG, or death due to any cause.

PFS will be analysed at the time of final ORR analysis, also at study close out if applicable, based on responses assessed by both IRC and investigator.

A summary of the assignments for progression and censoring dates for PFS are specified in [Table 4](#) below.

Table 4 Assignments for Progression and Censoring Dates for PFS Analysis

Situation	Date of Event (Progression/Death) or Censoring	Outcome Event (Progression/Death) Or Censored
No (or inadequate) baseline tumor assessments ^[1] and the subject has not died (if the subject has died follow the rules for death indicated at the bottom of the table)	Randomization	Censored
No post-baseline assessments and the subject has not died (if the subject has died follow the rules for death indicated at the bottom of the table)	Randomization	Censored
Progression documented without extended loss-to-follow-up time	Date of assessment of progression ^[1]	Event
No progression (or death)	Date of last 'adequate' assessment of response ^[2]	Censored
New anticancer treatment started (prior to documented disease progression or death) ^[3] .	Date of last 'adequate' assessment of response ^[2] (on or prior to starting anti-cancer therapy)	Censored
Death without extended loss-to-follow-up time	Date of death	Event
Death or progression after an extended loss-to-follow-up time (two or more missed cycles + 7 day window) ^[4]	Date of last 'adequate' assessment of response ^[2] prior to PD/death (prior to missed assessments)	Censored

Situation	Date of Event (Progression/Death) or Censoring	Outcome Event (Progression/Death) Or Censored
Death or progression after an extended loss-to-follow-up time from randomization	Date of randomization	Censored

[1] Adequate baseline assessment is defined as at baseline, a patient has at least one of the following measurements:
a. Serum M-protein ≥ 0.5 g/dL (≥ 5 g/L) or b. Urine M-protein ≥ 200 mg/24h or c. Serum FLC assay: Involved FLC level ≥ 10 mg/dL (≥ 100 mg/L) and an abnormal serum free light chain ratio (<0.26 or >1.65)

[2] An adequate assessment is defined as an assessment where the IRC/Investigator determined response is sCR, CR, VGPR, PR, MR, or SD.

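### The partial-date rule for new anti-cancer therapy protects the last PD assessment, not the first PD that defines the event, so a true PFS or TTP event can become a censoring

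*SAP*

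**What the plan says.** **Purpose of the imputed date.** SAP Section 15.7.2.1 says that start dates of follow-up therapy "will be temporarily imputed in order to define event and censoring rules for progression-free survival, response rate, time to progression, duration of response", and also for time to response. The imputed date therefore helps decide who has an event.

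**The rule when only the day is missing.**
- The first sub-rule begins "If partial date falls in the same month as the last dose of study treatment" and gives last dose + 1, capped at month end.
- The second covers a therapy month that is also the month of the last assessment. It reads "last assessment is PD, then assign to earlier of (date of PD+1, last day of month".
- A participant who meets both conditions gets whichever date is later.
- Everyone else falls to the default line: "Otherwise, impute missing day to the first of the month".

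A separate line covers dates that lack the month too: "If missing start day and month, then no imputation should be done".

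**The event date.** Sections 7.2.1.5 and 7.2.1.6 run PFS and TTP to the earliest confirmed PD. Table 3 in Section 7.1.1.1 assigns confirmed status at the first time point of a pair. A non-imaging PD needs confirmation by a later PD or by death due to PD. Note 1 limits confirming assessments to those before new therapy, "except for confirmation of PD, for which PD or death due to PD after new anti-cancer therapy are considered for confirmation of PD".

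**The censoring rule.** In Table 4, the row "New anticancer treatment started" (before progression or death) censors at the last adequate assessment on or before the therapy start. Table 5 does the same for TTP. The tie rule puts PD first only when both fall on the same day.

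**The concern.** The second sub-rule is plainly meant to stop a post-progression therapy from being dated before the progression. It does so for the last assessment. For a confirmed non-imaging PD, the last assessment is normally the confirming one, while the event belongs to the earlier one. If the two lie in different months, the first PD has no protection.

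The participants exposed are those who change therapy soon after first PD. Censoring them at the last adequate assessment before a progression that was observed is informative, and it lengthens PFS and TTP. It also undoes what Table 3 sets out to do, which is to keep a PD that is confirmed after new therapy has started.

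The loss would be hard to see. Section 15.7.2.1 says that the imputed therapy dates are not stored and that imputed dates are not shown in listings.

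**Working it through.** The SAP gives no figure to reproduce here. I applied the rule literally, taking the PD date in the second sub-rule as the date of the last assessment.

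**Worked dates (2019)**

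| | Last dose | First PD | True therapy start | Recorded as | Confirming PD | SAP date | Result | Keyed on first PD |
|---|---|---|---|---|---|---|---|---|
| A | 20 Feb | 13 Mar | 20 Mar | Mar | 3 Apr | 1 Mar | censored | 14 Mar, event |
| B | 4 Mar | 25 Mar | 29 Mar | Mar | 8 Apr | 5 Mar | censored | 26 Mar, event |

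- In A, neither the last dose nor the last assessment is in March, so the default line applies.
- In B, the last dose is in March, so the first sub-rule gives 4 Mar + 1.
- In both, the therapy is dated before the PD and the same-day tie rule does not help.

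**How often, given a missing start day**

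Inputs from the SAP:
- the imputation rules of Section 15.7.2.1;
- the 3-weekly assessment schedule in Section 15.5.4.

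Inputs that are assumed:
- first PD on each calendar day of 2019 in turn;
- last dose 21 days before first PD;
- therapy *t* days after first PD;
- confirming PD, which is also the last assessment, *c* days after first PD.

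The error needs the therapy in the PD month and the confirming PD in the next month. With month length L, the PD day must be at most L − t and greater than L − c. That is c − t days per month when c > t, and none otherwise. The share is therefore 12 × (c − t) / 365. For c = 21 and t = 3 this is 12 × 18 / 365 = 216/365 = 59.2%.

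| Confirmation c | t = 3 | t = 7 | t = 10 | t = 14 |
|---|---|---|---|---|
| 21 days | 59% (216/365) | 46% (168/365) | 36% (132/365) | 23% (84/365) |
| 14 days | 36% (132/365) | 23% (84/365) | 13% (48/365) | 0% |
| 7 days | 13% (48/365) | 0% | 0% | 0% |
| 3 days | 0% | 0% | 0% | 0% |

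Running the rule day by day gives the same counts. A 21-day gap crosses a month boundary on 252 of 365 days (69%).

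**Last dose on the day of first PD.** The first sub-rule then gives PD + 1, capped at month end, where the tie rule keeps the event. The share is 0% in every cell.

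**Second sub-rule keyed on the first PD.** The share is 0% in every cell.

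**The case against.** **The effect is narrow and may be zero.** Note 1 to Table 3 requires no minimum interval before confirmation, only a different sample, so confirmation within days is possible and the error then largely disappears. A dose given on the day of first PD removes it altogether. The rule also works when the first PD is the last assessment and falls in the therapy month, as with an imaging PD or a PD confirmed by death. A therapy started in a later month than the PD is not misdated before it. PFS and TTP are secondary and descriptive. All of this stands. It limits the size of the problem, but it does not make the rule right.

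**DoR.** A reader might infer that DoR is hit in the same way. Section 7.2.1.3 censors responders without confirmed PD, and the participants here do have confirmed PD. Section 15.7.2.1 names DoR and DoR borrows the Table 5 censoring times, so an effect is possible, but it is less explicit.

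**Primary ORR.** A reader might also infer that the year-only rule lets a response to the next therapy count for study drug. Section 7.1.1 already stops at the earlier of confirmed PD or new therapy. Such credit would need a year-only date, a switch without confirmed PD, and a first confirmed response on the next drug. Nothing in the SAP shows that this occurs, and no calculation supports it.

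**Filling in year-only dates.** Using last dose + 1, or 1 January if the last dose was in another year, would cause the same error on a larger scale. With last dose 21 days before PD and therapy 7, 14 or 28 days after it, that date precedes the PD in 98%, 96% and 92% of cases. Leaving the date missing keeps those events.

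**Conclusion.** The point holds for PFS and TTP. As written, Section 15.7.2.1 can date a therapy before the PD that preceded it, and Tables 4 and 5 then replace a true event with a censoring.

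The size is conditional and uncertain. It ranges from 0% to 59% of participants who have a missing start day and switch 3 to 14 days after first PD. The upper end needs confirmation about three weeks later and no dose at the first-PD visit. It is not 59% of the trial population: the SAP does not say how many therapy dates are partial, so no effect on a median can be computed. The direction is clear, since events are lost and PFS and TTP look longer.

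For DoR the effect is less explicit. The primary ORR test is not affected by this mechanism. The correction is worth making because the rule misses its own purpose and is cheap to repair.

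**What to change.** Replace the second sub-rule in Section 15.7.2.1 with: *if the partial date falls in the same month as the first documented PD that defines the event (the first of a confirmed pair, or an imaging PD), assign the earlier of that PD date + 1 and the last day of the month; apply this separately for IRC and investigator assessment.*

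Keep the rule that takes the later date when both sub-rules apply. Leave the year-only rule unchanged. Add a listing of participants whose event or censoring status depends on an imputed therapy date.

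The cost is one sentence of SAP text, a small change to the derivation and one short listing. PFS and TTP estimates may become slightly less favourable.
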